#### Description of the Modified Toxicity Probability Interval-2 Algorithm

The mTPI-2 algorithm employs a simple beta-binomial Bayesian model. The prior distribution for all dose levels is Beta(1,1). The posterior distribution for all dose levels is Beta(1+a, 1+b), where a and b are the number of participants with and without a DLT at the current dose level, respectively. The posterior density of the toxicity probability is divided into multiple intervals with equal length. These intervals are categorized as underdosing, proper dosing, and overdosing in terms of toxicity. The underdosing interval corresponds to a dose escalation, overdosing corresponds to a dose de-escalation, and proper dosing corresponds to staying at the current dose. Given an interval and a probability distribution, the unit probability mass of that interval is defined as the probability of the interval divided by the length of the interval. The design for the dose escalation phase of the study uses a target DLT rate of 30% and an equivalence interval (25%, 33%) for dose escalation/de-escalation decisions as well as MTD determination. A dose level will be considered unsafe, with no additional participants enrolled at that dose level, if it has an estimated 80% or more probability of exceeding the target DLT rate of 30% (ie, Probability  $[DLT > 30\% \text{ data}] \ge 80\%$ ) with at least participants treated and evaluated at that dose level. In Table 15, dose escalation/de-escalation decision rules are computed based on the above information.

Number		Number of Evaluable Participants Treated at Current Dose Level										
of DLTs	1	2	3	4	5	6	7	8	9	10	11	12 °
0	S a	S a	Е	Е	Е	Е	Е	Е	Е	Е	Е	Е
1	S b	S b	S e	S	Е	Е	Е	Е	Е	Е	Е	Е
2		DU d	DU	DU	D	D	S	S	Е	Е	Е	Е
3			DU	DU	DU	DU	DU	D	D	S	S	Е
4				DU	DU	DU	DU	DU	DU	D	D	D
5					DU							

 Table 15
 Modified Toxicity Probability Interval-2 Algorithm

a Changed from "E" to "S" as a minimum of evaluable participants are needed to make a dose escalation decision.

b Changed from "D" to "S" as a minimum of evaluable participants are needed to make a dose escalation decision.

c The "S" cells in original modified toxicity probability interval-2 algorithm are modified to either E or D according to whether the observed DLT rate is < or  $\ge$  the target toxicity of 30%, respectively.

d If at the first dose level, participants can choose to early terminate the trial or not based on their own discretion.

e Changed from "D" to "S" to ensure the mTPI-2 algorithm performs as conservatively as the standard 3+3 design if a single DLT is observed among the first 3 participants at a new dose level.

Note: Target toxicity (%) is 30% and equivalence interval (25%, 33%). The sample size cap for each dose level will be participants.

Abbreviations: D: de-escalate to the next lower-dose level; DLT: dose-limiting toxicity; DU: current dose is unacceptably toxic; E: escalate to the next higher dose level; S: stay at the current dose level. Sources: Modified from Guo et al, 2017 and Ji et al, 2010.

## 6.6.2 Dose Expansion

Participants enrolled in Part B Dose Expansion will receive sabestomig Q3W administered via IV infusion at the RP2D determined during Part A Dose Escalation.

The opening of Part B is dependent on emerging data from Part A. Cohorts B1 and B2 may open for enrollment either in parallel or sequentially at the discretion of AstraZeneca. The opening of Cohort B2 will be gated on emerging antitumor activity data from participants enrolled in Part A and/or Cohort B1.

## 6.6.3 Definition of Dose-limiting Toxicity

The DLTs will be evaluated during Part A Dose Escalation. The DLT evaluation period will be 28 days from the first dose of sabestomig on Cycle 1 Day 1. Participants who do not remain in the study for the entire duration of the DLT evaluation period, for reasons other than DLT, will be considered non-evaluable for DLT evaluation and will be replaced with another participant at the same dose level if needed to ensure a minimum of CCI evaluable participants in the ATD and mTPI-2 cohorts, respectively.

A DLT will be defined during Part A Dose Escalation as any  $\geq$  Grade 3 AE as per NCI CTCAE version 5 unless unequivocally due to underlying malignancy or an extraneous cause. The modifications and exceptions to this are detailed below.

The following conditions will be considered as DLTs:

- Any death not clearly due to the underlying disease or extraneous causes.
- Grade 4 imAE.
- Any  $\geq$  Grade 3 non-infectious pneumonitis irrespective of duration.
- Any  $\geq$  Grade 3 non-infectious colitis irrespective of duration.
- Liver transaminase elevation:
  - Isolated liver transaminase elevation > 5 x but  $\le 10$  x ULN that does not downgrade to AST/ALT  $\le 3$  x ULN or less within 7 days after onset with optimal medical management including systemic corticosteroids.
  - Transaminase elevation > 10 x ULN regardless of duration or reversibility.
  - Isolated TBL elevation > 3 x ULN that does not downgrade to ≤ 1.5 x ULN within 7 days after onset with optimal medical management (for participants with Gilbert's syndrome: TBL > 3 x ULN and doubling of direct bilirubin that does not downgrade to baseline value within 7 days).
  - Any increase in AST/ALT > 3 x ULN and concurrent increase in TBL  $\ge$  2 x ULN, regardless or duration or reversibility, where no other reason, other than the investigational product(s), can be found to explain the combination of increases (for participants with Gilbert's syndrome: TBL > 3 x ULN and doubling of direct bilirubin that does not downgrade to baseline value within 7 days).
- Any Grade 3 imAE, including rash, pruritus, or diarrhea (NOTE: this excludes colitis or pneumonitis, as these AEs are already defined above), that does not downgrade to Grade 2 or less within 7 days after onset of the event despite maximal supportive care including systemic corticosteroids.
- Grade 3 nausea, vomiting, or diarrhea that does not resolve to Grade 2 or less within 3 days of initiation of maximal supportive care.
- Neutropenia.
  - $\geq$  Grade 3 neutropenia, without associated fever or systemic infection, which does not improve by at least one grade within 7 days of onset.
- Thrombocytopenia:
  - Grade 4 thrombocytopenia lasting more than 7 days.
  - $\geq$  Grade 3 thrombocytopenia associated with a Grade  $\geq$  2 bleeding, which in the opinion of the Investigator, is related to study intervention.
- Grade 4 anemia not related to the underlying disease or any extraneous cause.

- Cytokine Release Syndrome (CRS):
  - Grade 4 CRS of any duration.
  - Grade 3 CRS that does not improve to Grade  $\leq 2$  within 72 hours.

The following conditions will not be considered as DLTs:

- Grade 3 fatigue lasting  $\leq$  7 days.
- Grade 3 endocrine disorder (thyroid, pituitary, and/or adrenal insufficiency) that is managed with or without systemic corticosteroid therapy and/or hormone replacement therapy with resolution of the symptoms within 14 days after treatment onset.
- Grade 3 inflammatory reaction attributed to a local antitumor response (eg, inflammatory reaction at sites of metastatic disease, lymph nodes) that resolves to ≤ Grade 1 within 7 days after onset.
- Vitiligo or alopecia of any AE Grade.
- Grade 3 or Grade 4 lymphopenia (unless associated with clinical sequelae).
- Grade 3 laboratory abnormalities that are not associated with clinical signs or symptoms (eg, hyperlipasemia or hyperamylasemia not associated with clinical signs or symptoms or radiographic features suggestive of pancreatitis) and are reversed with appropriate maximal medical intervention within 7 days.

Immune-mediated AEs are defined as AEs of an immune nature (ie, inflammatory) in the absence of a clear alternative etiology. In the absence of clinical abnormality, repeat laboratory testing will be conducted to confirm significant laboratory findings prior to designation as a DLT.

An AE not listed above or an AE meeting the DLT criteria above but occurring outside of the DLT-evaluation period, may be defined as a DLT after consultation with AstraZeneca and Investigators based on the emerging safety profile.

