Assessment of B-symptoms (Section 8.1.1)	Х				Х		X	
Assessment of adverse events and serious adverse events (Section 8.3)	÷			X-			→	
Concomitant medications (Section 6.5)	←			X-				
Blood and Urine Tests for Safety								
Chemistry (Section 8.2.7) f	X g	Х	Х	Х	Х		X	
Hematology (Section 8.2.7) f	X g	Х	Х	Х	Х		Х	
Cardiac troponin (Section 8.2.7) f				If clinica	ally indicated		·	
Glycated hemoglobin (Section 8.2.7)							C3D1, C5D1, C7D1, C9D1, C11D1, C13D1, C15D1, C17D1, C19D1, C21D1, C23D1, C25D1, C27D1, C29D1, C31D1, C33D1, and C35D1	

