C2D1, C3D1, and C4D1	Х	Х	Х	Х	Х			
C5D1, C6D1, etc.	Х			Х				

f All safety laboratory results must be reviewed by the Investigator or designee prior to sabestomig administration.

g If screening assessment was performed within the 5 days prior to C1D1 (Days -5 to -1), then the assessment does not need to be performed prior to SOI on C1D1.

h Free thyroxine and triiodothyronine only to be measured if thyroid-stimulating hormone is abnormal or if suspicion of an adverse event related to the endocrine system.

i Hepatitis B virology testing during treatment and follow-up is required for participants with positive HbsAg or isolated positive anti-hepatitis B core antibody (negative HbsAg and negative antibody to hepatitis B surface antigen) at screening and for any participant where clinically indicated. Participants with positive HbsAg must remain on antiviral therapy, per institutional practice, to ensure adequate viral suppression during the study intervention and follow-up periods. Controlled hepatitis B viral load is defined as serum hepatitis B virus DNA < 100 IU/mL by PCR.

Hepatitis C virology testing during treatment and follow-up is only required for participants with positive hepatitis C antibody at screening and for any participant where clinically indicated. Controlled hepatitis C viral load is defined as undetectable hepatitis C virus RNA by PCR either spontaneously or in response to a successful prior course of anti-hepatitis C therapy.

j Collection times for serum samples for PK on days of sabestomig administration are shown below. On days when sabestomig is not administered (C1D8, C1D15, and C2D8), only one serum sample for PK is required during the visit.

Collection Times for Serum Samples for PK on Sabestomig Dosing Days						
	Prior to SOI (within		Post EOI			
Cycle Number and Day	30 min prior to SOI)	EOI (+15 min)	4 h (± 15 min)	48 h (± 2 h)		
C1D1	Х	Х	Х	X (collected at C1D3 visit)		
C2D1, C3D1, C4D1, C5D1, C6D1, C8D1, C10D1, C14D1, C18D1, C26D1, C34D1, and CnD1 a	Х	х				

k On sabestomig dosing days, serum samples for ADA will be collected within 30 minutes prior to SOI and may be collected at the same time as the prior to SOI serum sample for PK.

 On sabestomig dosing days, the sample should be collected prior to start of sabestomig administration.

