# 4.1.1 Part A: Dose Escalation

Part A Dose Escalation will evaluate up to 8 dose levels of sabestomig and consist of up to participants with r/r cHL in order to determine a RP2D. Cohorts A1 to A4 will be single participant cohorts with 4 dose levels of sabestomig (2, 7, 22.5, and 75 mg) based on an ATD (Section 6.6.1.1). However, the operating model will switch to a mTPI-2 algorithm should a Grade 2 or greater TEAE occur during the DLT period (Section 6.6.1.2).

Cohorts A5, A6, and A7 for subsequent dose levels of sabestomig (225, 750, and 1500 mg) will enroll participants based on the mTPI-2 algorithm to establish the safety of sabestomig (Section 6.6.1.1). Based on emerging data, the optional Cohort A8 (at 2000 mg) may open and may also enroll up to participants. After a cohort is declared safe (eg, Cohort A5, A6, A7 or A8) and based on emerging safety, efficacy, PK and biomarker data, the cohort may be expanded (up to participants); the cohorts may be opened in parallel to fill their rosters of up to participants each (mini dose expansion).Intermediate dose levels (50, 150, 450, 1000, 1250, and 1750 mg) may be explored if warranted by emerging safety, PK, pharmacodynamic, biomarker, and response data (Section 6.6.1 and Table 14).

The planned starting dose will be 2 mg (dose level 1). Participants will be evaluated for DLTs during a 28-day DLT evaluation period. Refer to Section 6.6 for further details regarding the ATD, mTPI-2 algorithm, and DLT definitions.

Participants will receive sabestomig Q3W administered via IV infusion at the selected dose starting on Cycle 1 Day 1. All participants will be treated for a maximum of 35 cycles, until disease progression, unacceptable toxicity, withdrawal of consent, or other reason for discontinuation (Section 7).

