#### Table 9 Criteria for Adequate Organ and Marrow Function

Abbreviations: ECHO: echocardiogram; FEV1: forced expiratory volume over 1 second; LVEF: Left ventricular ejection fraction; MUGA: multigated acquisition scan; ULN: upper limit normal.

- a To receive subsequent cycles of sabestomig (from cycle 2 onwards) thresholds for adequate marrow, renal, and liver function must be met. Laboratory evaluations must be performed up to 3 days prior to initiation of each cycle of treatment; transfusion and granulocyte colony stimulating factor support is permissible.
- b Rostoker et al, 2007.
- c If clinically indicated, and at the Investigator's discretion, a consultation with a cardiologist is recommended for follow-up.
- d If assessed pulmonary function testing is only required for those eligible participants with pre-existing obstructive or fibrotic lung conditions.

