#### 6.6.1.1 Accelerated Titration Design

For dose levels < 225 mg (Cohorts 1 to 4), dose escalation will follow an ATD and will be participant cohorts. Cohorts 5, 6, 7, and the optional last cohort, Cohort 8, will follow an mTPI-2 and will consist of COM participants. The enrolled participants must complete the DLT evaluation period before a dose escalation decision is made by the SRC.

At any ATD dose level, dose escalation will switch from ATD dose escalation to the mTPI-2 dose escalation algorithm if the initially enrolled participant has any of the following during the DLT evaluation period:

- Any DLT.
- Any  $\geq$  Grade 2 TEAE.

Once the mTPI-2 algorithm is triggered, all further dose escalation will follow mTPI-2 algorithm.

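### Part A's 28-day DLT window includes dose 2, but no chemistry or hematology is scheduled after that dose until about Day 43, so silent laboratory DLTs are not tested for before escalation is allowed

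*Protocol*

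**What the plan says.** - **Window.** Protocol Section 6.6.3: "The DLT evaluation period will be 28 days from the first dose of sabestomig on Cycle 1 Day 1". Under Section 6.6.6 a dosed participant is evaluable after completing the 28 days or having a DLT. No laboratory result after dose 2 is asked for.
- **Dosing.** Protocol Section 4.1.1: "Participants will receive sabestomig Q3W administered via IV infusion at the selected dose starting on Cycle 1 Day 1".
- **Laboratory schedule.** In Table 2 (Part A) the chemistry and hematology rows are marked at C1D1, C1D3, C1D8, C1D15, C2D1 and then from C3D1 onward. Both C2D8 cells are blank. C2D8 is nevertheless a full visit, with physical examination, vital signs, ECG, PK, ADA and biomarker samples. Footnote j says of PK sampling: "On days when sabestomig is not administered (C1D8, C1D15, and C2D8), only one serum sample for PK is required during the visit".
- **The C2D1 sample precedes dose 2.** Table 2 footnote f: "All safety laboratory results must be reviewed by the Investigator or designee prior to sabestomig administration". Table 9 footnote a adds: "Laboratory evaluations must be performed up to 3 days prior to initiation of each cycle of treatment".
- **SAP Appendix B, Part A.** Hematology/chemistry has Days 19-32 for C2D1, nothing for C2D8, and Days 33-53 for C3D1. Physical examination/vital signs and ECG do have a C2D8 window, Days 26-36.
- **Decision point.** Protocol Section 6.6.1.1: "The enrolled participants must complete the DLT evaluation period before a dose escalation decision is made by the SRC". Nothing requires waiting for the C3D1 results.

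**The concern.** Several DLT criteria in Section 6.6.3 can be met on laboratory values with no symptom. DLT counts drive the mTPI-2 decisions in Table 15, and DLT incidence is a Part A primary endpoint. The window is long enough to take in the first week after dose 2, yet no blood test is scheduled in that week. A participant can therefore be counted as evaluable and free of DLT although the laboratory criteria were not checked after the second dose. Any DLT missed this way lowers the count, so the interim escalation decision can be wrong only in the direction of escalating.

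**Working it through.** **1. Timeline (Day 1 = first dose, every 3 weeks).**
- C2D1 = 1 + 21 = Day 22 (±1 day: Days 21-23).
- C2D8 = 22 + 7 = Day 29 (±3 days: Days 26-32).
- C3D1 = 1 + 42 = Day 43 (±3 days: Days 40-46).
- Window days from dose 2 on: 28 - 22 + 1 = 7 (6 to 8 with the ±1 day).
- Scheduled chemistry or hematology after dose 2 within the window: 0.
- Next scheduled sample: 43 - 28 = 15 days after Day 28, or 40 - 28 = 12 at the earliest.
- Gap between scheduled samples: 43 - 22 = 21 days, or 43 - 19 = 24 if the C2D1 sample is taken 3 days early.

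**2. Is the blank cell real?** Protocol Table 2 and SAP Appendix B are separate tables. Both omit hematology/chemistry at C2D8 while keeping other assessments there. The gap is in the plan and does not come from how the text was read.

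**3. Which criteria are exposed (Section 6.6.3).**
- Settled by the values at one time point: transaminases above 10 x ULN; AST/ALT above 3 x ULN with bilirubin at least 2 x ULN and no other explanation; Grade 4 anemia not due to disease or another cause.
- Needing about 7 days of persistence: transaminases above 5 and up to 10 x ULN; isolated bilirubin above 3 x ULN; afebrile Grade 3 or higher neutropenia; Grade 4 thrombocytopenia. With onset on Day 22 the 7 days end on 22 + 7 = Day 29, so these generally cannot be settled by Day 28 on any schedule. What is lost for them is the record of onset.

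**4. Table 15 reproduced.** Model: posterior Beta(1 + x, 1 + n - x); intervals of width 0.33 - 0.25 = 0.08; decision by the largest unit probability mass; DU if P(p > 0.30) is at least 0.80. Rows 0 to 4 for n = 1 to 12 agree with the printed table except in cells that its footnotes say were changed: 0/1, 0/2, 1/1, 1/2, 1/3 and 3/12. For three participants:

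| DLTs | P(p > 0.30) | Algorithm | Table 15 |
|---|---|---|---|
| 0/3 | 0.240 | E | E |
| 1/3 | 0.652 | D | S (footnote e) |
| 2/3 | 0.916 | DU | DU |

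**5. Effect of one undetected DLT.** A true 1/3 is recorded as 0/3, and the decision moves from S to E. In a single-participant accelerated titration cohort, Section 6.6.1.1 switches to mTPI-2 on any DLT or any Grade 2 or higher TEAE. One undetected laboratory event of that kind means no switch.

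**6. Illustration only.** Let p be the true DLT rate and f the share of DLTs that are silent, laboratory-only and arise after dose 2. The documents do not give f, so the values below are assumptions. The recorded rate is q = p(1 - f), and the chance of escalating on the first three is (1 - q)^3. Example: p = 0.40 and f = 0.10 give q = 0.36 and 0.64^3 = 26.2%.

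| p | f = 0 | f = 5% | f = 10% |
|---|---|---|---|
| 30% | 34.3% | 36.6% | 38.9% |
| 40% | 21.6% | 23.8% | 26.2% |
| 50% | 12.5% | 14.5% | 16.6% |

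**The case against.** The plan has safeguards. Adverse events are collected throughout, and C2D8 includes a clinical examination. Section 8.2.7 allows extra samples when clinically indicated. Section 6.6.3 lets an event found outside the window be classed as a DLT. Section 6.6.7 has the SRC review all available data before each decision, with cumulative analyses for late toxicity once at least 6 participants have completed at least 2 cycles and again before Part B. Dose 2 itself requires laboratory values within the Table 9 limits, so participants enter the last week of the window having just passed a screen. The protocol and SAP also agree with each other, so this is a choice of monitoring intensity and not a contradiction between them.

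Much of this stands. It rules out saying that these DLTs go unseen: symptomatic events can be found in time, and C3D1 results can be acted on later. It does not close the gap at the interim decision. The examination measures neither blood counts nor liver tests. Discretionary sampling depends on a clinical trigger, which a silent event does not give. The SRC cannot review results that were never obtained. The late-DLT clause is permissive, and the C3D1 result can arrive after the cohort has escalated. The cumulative reviews do not gate each cohort.

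A further fair objection is that C2D8 is nominally Day 29 and one sample cannot settle the 7-day criteria. That limits what the fix achieves, but the sample would still serve the single-time-point criteria and show the onset of the others.

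**Conclusion.** The point holds for asymptomatic laboratory DLTs arising after dose 2, at interim escalation in Part A. No scheduled test looks for them before the SRC may decide, and the bias is toward escalation. It assumes dose 2 is given on schedule; if dose 2 is delayed past Day 28, the point does not apply to that participant. The size cannot be derived from the documents. The percentages in step 6 show direction and rough scale under assumed values of f.

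Three stronger readings are tempting and not supported:
- **That a quarter of laboratory DLTs are missed, because 7/28 = 25%.** This needs onset spread evenly over the window. The laboratory screen before dose 2 makes that doubtful, and the persistence criteria mostly could not be settled by Day 28 anyway.
- **That a cohort rated DU could be recorded as E.** This needs two silent, laboratory-only, post-dose-2 DLTs among three participants. Nothing in the documents makes that likely.
- **That the final MTD is biased to the same degree.** The MTD is estimated by isotonic regression after escalation is completed (Section 9.4.3.1). Most C3D1 results would exist by then and late events may be counted. The RP2D rests on the totality of the data (Section 6.6.5).

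**What to change.** - In Protocol Table 2 (Part A), mark chemistry and hematology at C2D8, nominally Day 29 and so 28 days after the first dose.
- In SAP Appendix B (Part A), add the matching C2D8 window for hematology/chemistry. The existing vital-signs column offers a consistent split: C2D1 Days 19-25, C2D8 Days 26-36, C3D1 Days 37-53. This edit only keeps the visit tables in order; detection comes from the sample.
- Reconcile Sections 6.6.3 and 6.6.6 with Table 2. State how a sample taken on Days 26-32 relates to the 28-day period, and that its result is available to the SRC before the escalation decision. The DLT criteria need no change.

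Cost: one local blood sample per Part A participant at a visit where blood is already drawn, edits to two protocol sections, Table 2 and the SAP, and possibly a few days' wait for the result before a cohort decision.

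The documents do not say whether escalation is already complete. If it is, the CSR should state that laboratory testing after dose 2 within the DLT window was unscheduled.
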